3.5.2.7 Pregnancy

Pregnancies will be recorded during the whole trial. Females who become pregnant during the trial must stop participation in the trial. In case of pregnancy the subject or female partners of male subjects will be followed-up until the pregnancy outcome is known. The Investigator must notify the Sponsor of any pregnancy.

The Investigator must actively follow-up, document and report on the outcome of all pregnancies, even if the subjects are withdrawn from the study.

3.5.3 Total of Blood Volume

Table 4 presents the number and volume of blood samples and the total volume of blood that will be collected throughout the trial per patient and trial part.

Table 4. Number and Volume of Blood Samples and Total Blood Volume Collected per Patient

Assessment	Maximum # samples	mL of blood per sample	Total volume of blood (mL)
Clinical laboratory	3	8	24
Clinical Chemistry			
Hematology			
ADA	2	4	8
Pharmacokinetics	15	3	45
ilofotase alfa			
Pharmacodynamics	15	14	210
Total volume of blood drawn			287

3.5.4

Timing of Assessments

The actual times of all assessments will be recorded in the eCRF.

For PK blood sampling, post dose blood samples may be collected within ± 5 minutes of the scheduled time for samples the first 8 hours post dose, within ± 60 minutes of the scheduled time for all other samples.

For safety assessments, pre-dose assessments on day 1 will also be performed between waking up and dosing. Sampling for clinical laboratory assessments at screening and post-dose at day 10 does not have a time-window.

In the event assessments are planned for the same scheme time, the order of the assessments should be arranged in such a way that PK blood sampling is done exactly on time, in practice generally vital signs will be done first, followed by blood sampling (exactly on time), followed by safety laboratory sampling. Baseline is defined as measurements taken on day -2, day -1 and day 1. Measurements taken on day 1 must be taken at any time up to immediately before randomization to be considered as baseline measurements. Measurements taken at or after randomization are not considered baseline measurements.

3.6

Statistical Procedures

3.6.1

Trial Populations

Intention to Treat population (ITT)

All randomized patients will be included in the ITT population.

Population for the safety analysis (SAS)

All patients who have received trial medication.

Population for the PK analyses (PKS)

All patients who have received ilofotase alfa and for whom sufficient bioanalytical data are available to calculate reliable estimates of the PK parameters.

3.6.2

Statistical Evaluations

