Trial drug (ilofotase alfa) is provided in glass vials as a concentrate for infusion (aqueous buffer at a pH of 7.0). Prior to administration, the trial drug will be diluted with sterile sodium chloride 0.9% for injection (isotonic saline), United States Pharmacopeia (USP) / European Pharmacopoeia (EP) or equivalent, to a final volume of 50 mL and administered as an iv infusion using a dosing syringe. Trial drug will be administered as a 1-hour continuous iv infusion via a peripheral access point.

Prohibited Medication during the trial period

1. NSAIDs
2. Corticosteroids
3. Compounds intended to interfere with bone metabolism (e.g. Denosumab, Teriparatide, Romosozumab, Raloxifene)
4. Bisphosphonates
5. Supplements including Vitamin B6
6. Asfotase alfa

If there is a clinical indication to start any of these above medication, the subject should be withdrawn from the trial. Subjects who initiate any of the medication mentioned above during the trial period will be considered dropouts.

Criteria for evaluation

Primary endpoints

PPi and PLP serum concentration levels – recorded on day 1 (post dose) trough day 10 (inclusive).

A composite endpoint of the lowest serum concentration level of each of PPi and PLP will be created.

Exploratory endpoints

Pharmacokinetics: ilofotase alfa serum concentrations measured between day 1 and day 10 (inclusive).

Safety: Adverse events (AE) measured between day 1 and day 15 (inclusive).

	Vital signs (including supine systolic and diastolic blood pressure, pulse, body temperature, respiratory rate) measured at screening, on day 1, and on day 10.
	Clinical laboratory (including clinical chemistry, hematology, and urinalysis) tests, physical examination measured on day 1 and day 10 and listed in footnotes 6 and 7 of Table 1.
	Presence of anti-ilofotase antibodies detected on day 10.

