3.5.1 Pharmacokinetic Measurements

3.5.1.1 Ilofotase alfa concentration

Blood samples of 3 mL will be collected via an indwelling iv catheter or by a direct venipuncture at the time points indicated in Table 3 (see also Schedule of Assessments presented in Table 1).

The time clock (zero hours) starts at commencement of the iv dose of ilofotase alfa. The 60 minutes, 2-, 4- and 8-hours post dose blood samples may be collected within ±5 minutes of the scheduled times,

within ± 60 minutes for all the other scheduled times. The exact times of blood sampling will be recorded in the eCRF.

Table 3. PK sample schedule for determination of ilofotase alfa

Pre-dose	day 1	Pre-dose (2 samples)
Post infusion	day 1	60 min (immediately post dose) 2h 4h 8 h
	day 2	24 h
	day 3	48 h
	day 4	72 h
	day 5	96 h
	day 6	120 h
	day 7	144h
	day 8	168 h
	day 9	192 h
	day 10	216 h

Note: The 60 minutes sample is to be taken from the arm NOT used for infusion.

PK samples will be analyzed by a central laboratory. Processing, storage, and shipment of the samples are described in detail in the Laboratory Manual.

3.5.2

Safety and Tolerability Measurements

Safety and tolerability assessments will consist of AEs, and results of vital signs, clinical laboratory tests, physical examinations, and anti-drug antibodies (ADA). Assessments will be performed in accordance with the schedule of assessments. The actual times of all assessments will be recorded in the eCRF.

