3.5.2.2 Vital Signs

During the trial, blood pressure and pulse will be recorded after 5 minutes of rest in the supine position and after 2 minutes of rest in the standing position. These assessments will be made using an automated device. Body temperature and respiratory rate will be measured subsequently or at the same time as blood pressure and pulse.

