3.6.2.1 Primary endpoint

This analysis will use the intention to treat (ITT) analysis set.

Biochemical markers of HPP (PPI, and PLP) will be recorded for each patient at baseline (days -2, -1 and 1 before randomization) and after treatment, starting on day 1 and ending on day 10. PPI, and PLP levels will be listed and summarized for each of day 1 to day 10, overall and by trial arm. The median (minimum, maximum), mean, standard deviation (SD) and standard error of the mean (SEM) PPI, and PLP levels will be described overall and by trial arm. These data will also be displayed graphically.

For both PPI, and PLP the mean change and percentage change from baseline (with SD) will be tabulated per study day and by trial arm and shown graphically. The baseline value will be defined as the median value of the measurements prior to randomization.

The maximum change from baseline will be tabulated (median, minimum, maximum, mean (including SD, SEM and 95% confidence interval)) and shown graphically (mean, SD and 95% confidence interval) overall and by trial arm.

3.6.2.2 Exploratory endpoints.

Endpoints as listed under exploratory objectives will be listed and summarized, overall and by trial arm, using descriptive statistics by scheduled time point. No statistical tests will be performed on exploratory endpoints.

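### Vital signs are a safety endpoint of a one-hour infusion, but no reading is required between the start of infusion and day 10

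*Protocol*

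**What the plan says.** The protocol's synopsis lists vital signs (blood pressure, pulse, temperature, respiratory rate) among the exploratory safety endpoints, "measured at screening, on day 1, and on day 10". In Table 1 the vital-signs row has one mark on day 1, no footnote giving hours, and no mark on days 2 to 9.

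Section 3.5.2.2 fixes the method. On pulse and blood pressure it states that these "will be recorded after 5 minutes of rest in the supine position and after 2 minutes of rest in the standing position". It covers the equipment too: "These assessments will be made using an automated device". It gives no clock time.

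Section 3.5.4 says of day 1: "For safety assessments, pre-dose assessments on day 1 will also be performed between waking up and dosing". Where assessments share a planned time, it adds that "in practice generally vital signs will be done first, followed by blood sampling (exactly on time), followed by safety laboratory sampling".

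For pharmacokinetics the protocol is exact. In section 3.5.1.1, "The time clock (zero hours) starts at commencement of the iv dose of ilofotase alfa". Draws are fixed at 60 minutes and at 2, 4 and 8 hours on day 1, with a window of ±5 minutes.

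On analysis, section 3.6.2.2 states: "Endpoints as listed under exploratory objectives will be listed and summarized, overall and by trial arm, using descriptive statistics by scheduled time point". Section 3.6.2.6 has vital signs listed and, where applicable, described.

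**The concern.** The safety profile of a single intravenous dose is a stated objective (section 2), and section 3.6.2.4 names vital signs among the data on which tolerability will be judged. An infusion effect on blood pressure, pulse, temperature or breathing would be expected during the infusion or in the hours after it. A protocol that requires only a pre-dose value and a day 10 value can be followed to the letter and yield no vital-sign information for that period in either arm. The descriptive comparison of 0.8 with 3.2 mg/kg would then rest on values taken before the drug and about nine days after it.

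This is not a detail that can wait for an analysis plan. Assessment times belong in the protocol's schedule, and an analysis plan cannot recover readings that were not taken.

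**Working it through.** The protocol gives no figure to reproduce here. The check is a count of what each provision requires, followed by two timing sums.

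**1. Vital-sign readings required between start of infusion and day 10**

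- Synopsis: gives days only (screening, day 1, day 10).
- Table 1: one day 1 mark without an hour, and none on days 2 to 9. In the text at hand the row's last mark falls under day 15 rather than day 10. Columns may have shifted in extraction, so nothing rests on that mark, and under either position nothing is required in the interval.
- Section 3.5.2.2: posture and rest, no time.
- Section 3.5.4, timing sentence: times the pre-dose assessments. It does not say that day 1 safety assessments are pre-dose only, but it sets no later time.
- Section 3.5.4, ordering sentence: applies only when two assessments share a planned time. On day 10 it has a post-dose use, because vital signs and the 216 h draw fall on the same day. On day 1 no vital-sign time after dosing is set, so there is nothing to order.

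Result: 0 required readings. One pre-dose set on day 1 meets every provision.

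**2. Contrast with other day 1 measurements after the start of infusion**

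| Measurement | Fixed times | Count |
|---|---|---|
| Pharmacokinetics (3.5.1.1, Table 3) | 60 min, 2, 4, 8 h | 4 |
| PPi and PLP (3.4.1, Table 1 footnote 8) | 2, 4, 8 h | 3 |
| Vital signs | none | 0 |

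Staff are therefore already at the patient four times.

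**3. Smallest data set that complies**

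Per patient: screening, pre-dose on day 1, day 10. Acute values per arm: 6 × 0 = 0. The last draw before discharge is at 216 h, and 216 / 24 = 9 days after the start of infusion.

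**4. Would a set at 60 minutes disturb the pharmacokinetic draw?**

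The window is 60 ± 5, that is 55 to 65 minutes. One full set needs 5 + 2 = 7 minutes of rest.

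- Rest begun when the infusion stops: 60 + 7 = 67 minutes, which is 2 minutes too late.
- Supine rest begun at 55 minutes: supine reading at 60, standing reading at 55 + 7 = 62, leaving 65 − 62 = 3 minutes for measuring and drawing. An earlier start leaves more.

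Nothing in the protocol bars supine rest during the infusion, so the section 3.5.2.2 method fits.

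**5. Which clock?**

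Section 3.5.1.1 counts from the start of dosing, so 2, 4 and 8 h are 1, 3 and 7 h after a 60-minute infusion ends. Table 1 footnote 6 counts the same draws from the infusion itself. Read as hours after its end, they fall at 3, 5 and 9 h from the start. The two readings differ by 1 hour, so vital signs tied to these contacts need one clock.

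**The case against.** The strongest case is that this asks for denser sampling than an exploratory pilot needs. The endpoint is descriptive and untested, and there is no placebo arm, so a transient change in one of six patients could not readily be attributed to the drug. Section 1.1.3 reports single infusions up to 3.2 mg/kg as well tolerated in healthy volunteers, and section 3.1.5 relies on prior use to dose both arms in parallel. Section 1.2.1 promises close medical monitoring, patients stay in the centre to day 10 (3.1.3), dosing is supervised (3.3.12), and patients are asked about adverse events before and after dosing (3.5.2.1).

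Most of this stands, and it sets the size of the point. It does not remove it. Those provisions should catch a symptomatic reaction. Appendix 7.1 also lets an abnormal vital sign count as an adverse event, but only if someone measured it. Prior experience lowers the expected risk without supplying this trial's endpoint data, and section 1.1.3 mentions no earlier patients with hypophosphatasia.

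A second objection is that a post-dose reading taken on clinical judgement would not be lost. That is right. Section 3.5.4 records actual times and section 3.6.2.6 lists vital signs, so with six patients per arm each such reading would be visible. A reader might infer from the rule on summarising by planned time that such readings would be discarded. The protocol does not support that. They would only lack a planned time at which to be summarised and compared by arm.

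**Conclusion.** The point holds as a minor one: a cheap improvement, not an error that affects a result. The protocol requires no vital-sign reading between the start of infusion and day 10, so the by-arm data may contain no acute value. The loss is confined to standardised capture of acute, mainly asymptomatic changes at 0.8 versus 3.2 mg/kg. The primary analysis of PPi and PLP is unaffected.

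Two stronger readings should be resisted:

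- A reader might infer that post-infusion vital signs are excluded or that patients are left unobserved. Neither follows: such readings are not forbidden, and the monitoring provisions are real.
- A reader might want a probability of missing an effect. The documents give no rate of vital-sign change and no threshold for one, so any such figure would rest wholly on assumed values, and the point does not need it.

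The conclusion assumes only that the protocol is followed as written and that no other study document fixes post-dose times. Section 3.5.2 refers to the schedule of assessments for them.

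**What to change.** In Table 1 (by footnote) and section 3.5.4:

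- Specify one pre-dose vital-sign set on day 1, and post-dose sets at the existing draws at end of infusion (60 min), 2, 4 and 8 h.
- Time all of them from the start of infusion, as section 3.5.1.1 does ("The time clock (zero hours) starts at commencement of the iv dose of ilofotase alfa"), and align Table 1 footnote 6 to that clock.
- Keep the supine and standing method of section 3.5.2.2 and the vital-signs-first order of section 3.5.4. Start the supine rest ahead of each contact (before the infusion ends for the 60-minute set), so that every draw stays within ±5 minutes.
- List the values, and summarise change from pre-dose by time and arm, without tests.

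Cost:

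- Recordings: 4 × 12 = 48 at most, or 24 per arm.
- Rest: 4 × (5 + 2) = 28 minutes per patient, and 28 × 12 = 336 minutes (5.6 h) over the trial. If the standing reading were dropped at 60 minutes, it would be 5 + 3 × 7 = 26 minutes per patient.
- Measuring time comes on top, and the protocol does not state it.
- Four time points are added to the eCRF. Patients are already resident and attended at these times, so no blood or visit is added.

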3.6.2.1 Primary endpoint

This analysis will use the intention to treat (ITT) analysis set.

Biochemical markers of HPP (PPI, and PLP) will be recorded for each patient at baseline (days -2, -1 and 1 before randomization) and after treatment, starting on day 1 and ending on day 10. PPI, and PLP levels will be listed and summarized for each of day 1 to day 10, overall and by trial arm. The median (minimum, maximum), mean, standard deviation (SD) and standard error of the mean (SEM) PPI, and PLP levels will be described overall and by trial arm. These data will also be displayed graphically.

For both PPI, and PLP the mean change and percentage change from baseline (with SD) will be tabulated per study day and by trial arm and shown graphically. The baseline value will be defined as the median value of the measurements prior to randomization.

The maximum change from baseline will be tabulated (median, minimum, maximum, mean (including SD, SEM and 95% confidence interval)) and shown graphically (mean, SD and 95% confidence interval) overall and by trial arm.

3.6.2.2 Exploratory endpoints.

Endpoints as listed under exploratory objectives will be listed and summarized, overall and by trial arm, using descriptive statistics by scheduled time point. No statistical tests will be performed on exploratory endpoints.

3.6.2.3 Pharmacokinetic Evaluation

The PK serum concentration will be plotted versus time by treatment (individually, combined individual data and geometric mean). All individual data will be listed and described descriptively. The PK parameters and their statistical evaluation will be separate from the Clinical Trial Report of this trial. A separate analysis may include data of this trial in the existing population PK (PopPK) models to evaluate clearance (CL) and volume of distribution (Vd), which will be reported separately.

3.6.2.4 Evaluation of Safety and Tolerability Parameters

The Principal Investigator will evaluate the safety and tolerability of the treatment applied during the trial. This evaluation will consider the recorded AEs, vital signs, clinical laboratory, physical examination findings, and any other parameter that is relevant for safety assessment.

3.6.2.5 Adverse Events

All AEs reported will be coded and classified according to MedDRA. A listing will be given of all individual AEs. Summary tables of treatment emergent AEs (TEAEs) will be presented per treatment by system organ class and preferred term based on the MedDRA terminology list: one containing the number of TEAEs (frequency of occurrence, number and percentage of patients experiencing the event) by treatment and severity (intensity) and another containing the number of treatment related TEAEs (frequency of occurrence, number and percentage of patients experiencing the event) per treatment and severity. Additional total counts by treatment and relationship, and by treatment and severity will be given.

3.6.2.6 Vital signs

Vital signs will be listed, and they will be presented descriptively, where applicable.

3.6.2.7 Physical Examination

Changes from baseline for physical examination will be described and listed.

3.6.2.8 Anti-Drug Antibodies

ADA data will be listed. Any patient who is found to have antibodies against ilofotase alfa measured at day 10 and showing an increase from baseline will be considered positive for antibodies. Tables showing the number (and percentage) of patients who were positive at baseline (by trial arm and overall) and who were positive by day 10 (by trial arm and overall) will be shown using the ITT analysis set. Also, a table showing the number of patients who became positive by day 10 having been negative at baseline will be shown (by trial arm and overall).

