Safety will be assessed by examining the incidence of adverse events, serious adverse events and will be categorized by Medical Dictionary for Regulatory Activities (MedDRA) System Organ Class (SOC) and Preferred Term (PT) and will be summarized by trial arm and overall. Physical examination findings will be reported by trial arm and overall using the safety analysis set (SAS). For adverse events, seriousness, severity, relationship to trial drug and whether leading to trial drug discontinuation or application of any emergency remedy will be displayed.

Anti-ilofotase alfa antibodies

Any patient who is found to have antibodies against ilofotase alfa measured at day 10 and showing an increase from baseline will be considered positive for antibodies. Tables showing the number (and percentage) of patients who were positive at baseline (by trial arm and overall) and who were positive by day 10 (by trial arm and overall) will be shown using the ITT analysis set. Also, a table showing the number of patients who became positive by day 10 having been negative at baseline will be shown (by trial arm and overall).

Table 1. Schedule of Assessments

Visit	Pre-Treatment		Treatment	Follow up									
	day -2	day -1		day 2	day 3	day 4	day 5	day 6	day 7	day 8	day 9	day 10 /early withdrawal ¹	day 15
Trial day			day 1 ¹⁰										
Informed consent	X												
Eligibility check ²	X		X										
Medical history	X												
Demographics	X												
Physical examination	X		X									X	
Body weight + height ³	X		X										
Pregnancy test ⁴	X		X										X
Defining FSH level ⁵	X												
Safety laboratory	X		X										X
12-lead ECG	X												
Vital signs	X		X										X
Randomization			X										
Trial drug administration			X										
PK			X ⁶	X	X	X	X	X	X	X	X	X	X
PPi, PLP ⁷	X	X	X ⁸	X	X	X	X	X	X	X	X	X	X
Urine samples ⁹	X	X	X	X	X	X	X	X	X	X	X	X	X
Exploratory biomarkers ¹⁰	X	X	X	X	X	X	X	X	X	X	X	X	X
ADA samples			X										X
Previous and concomitant medication	X		X	X	X	X	X	X	X	X	X	X	
AE monitoring ¹¹			X	X	X	X	X	X	X	X	X	X	X

¹ Women of child bearing potential having day 10 assessment done on their early withdrawal date will need to be tested for pregnancy

² Check against inclusion and exclusion parameters

³ Body weight and length will be used to calculate the body mass index (BMI), height only at screening

⁴ Only for women of childbearing potential

⁵ Only for postmenopausal women

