3.6.3 Determination of Sample Size

No formal sample size calculation is provided as the purpose of this trial is exploratory. Up to twelve patients will be randomized, 6 to each trial arm. If this randomization rate is not achieved in a reasonable timeframe, the Sponsor will review the required sample size.

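### The day 10 anti-drug antibody percentages are placed on the ITT set rather than the protocol's own safety set, so they are diluted if a randomized patient is undosed or untested and kept in the denominator

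*Protocol*

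**What the plan says.** **Analysis set for ADA.** Section 3.6.2.8 and the matching synopsis paragraph promise tables of the number and percentage of patients positive at baseline, and of those "who were positive by day 10 (by trial arm and overall) will be shown using the ITT analysis set". A third table gives the number of patients who turn positive after a negative baseline; no percentage is mentioned for it.

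**Definitions.** Section 3.6.1 defines ITT without a dosing condition: "All randomized patients will be included in the ITT population". The same section defines the safety set (SAS): "All patients who have received trial medication".

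**Status of ADA.** The synopsis lists under the safety endpoints: "Presence of anti-ilofotase antibodies detected on day 10". Section 3.5.2 also counts ADA among the safety and tolerability assessments, beside adverse events, vital signs, laboratory tests and physical examination. The synopsis assigns the physical examination findings to the SAS.

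**Positivity rule.** Antibodies against the drug must be "measured at day 10 and showing an increase from baseline will be considered positive for antibodies" (section 3.6.2.8).

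**Size.** Section 3.6.3: "Up to twelve patients will be randomized, 6 to each trial arm".

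**The concern.** ITT protects a randomized comparison from selection after randomization. An ADA rate has a different purpose: it says how often exposure to the drug is followed by antibodies.

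- A patient who was randomized but never infused cannot develop antibodies in response to the drug.
- A patient without a day 10 result cannot meet the positivity rule, so the true status is unknown rather than negative.
- If either stays in the denominator, the day 10 percentage can only fall, which is the wrong direction of error for a safety rate.
- A table by randomized arm would also show a patient given the other dose under the dose not received.

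The protocol already has a better set and uses it for another safety item. It gives no reason for treating ADA differently. This is a choice written into the protocol, not a detail left open. At stake is how well the reported percentage describes patients who were exposed and tested. Section 1.2 calls the trial a pilot for a potential Phase 2/3 trial.

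**Working it through.** The protocol states no ADA rate, dropout rate or sample size calculation, so it has no figure to reproduce. The stated numbers agree with each other: 2 × 6 = 12.

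**Inputs from the protocol.** N = 6 per arm and N = 12 overall (section 3.6.3).

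**Assumed inputs, not in the protocol.** m = 0 to 2 randomized patients who are undosed or lack a day 10 result, and x = 1 to 3 positive patients.

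**Formulas.**
- ITT percentage, with such patients kept in the denominator: x/N.
- Percentage among dosed patients with a result: x/(N − m).
- Relative reduction: 1 − [x/N] ÷ [x/(N − m)] = 1 − (N − m)/N = m/N. It does not depend on x, provided x is at least 1.

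**Results** (ITT against evaluable patients):

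| N | m | x = 1 | x = 2 | x = 3 | m/N |
|---|---|---|---|---|---|
| 6 | 0 | 16.7% / 16.7% | 33.3% / 33.3% | 50.0% / 50.0% | 0 |
| 6 | 1 | 16.7% / 20.0% | 33.3% / 40.0% | 50.0% / 60.0% | 1/6 |
| 6 | 2 | 16.7% / 25.0% | 33.3% / 50.0% | 50.0% / 75.0% | 1/3 |
| 12 | 1 | 8.3% / 9.1% | 16.7% / 18.2% | 25.0% / 27.3% | 1/12 |
| 12 | 2 | 8.3% / 10.0% | 16.7% / 20.0% | 25.0% / 30.0% | 1/6 |

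One such patient shifts the rate by 3.3 to 10.0 points in an arm and by 0.8 to 2.3 points overall. Two shift it by 8.3 to 25.0 points in an arm and by 1.7 to 5.0 points overall.

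**Would the safety set alone be enough?** No. Take an arm of 6 with one undosed patient, one patient dosed but without a day 10 result, and two positives (assumed counts). ITT gives 2/6 = 33.3%, the safety set gives 2/5 = 40.0%, and dosed patients with a result give 2/4 = 50.0%. The safety set removes only the undosed patient.

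**Against sampling error.** The exact 95% confidence interval for 2/6 runs from 4.3% to 77.7%, far wider than any of these shifts.

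**The case against.** The strongest reply is that the ITT and dosed-and-tested groups will probably be the same patients. Randomization comes immediately before dosing (section 3.3.8). Treatment is a single supervised infusion with the volume checked (sections 3.3.4 and 3.3.12). Patients stay at the center until day 10 (section 3.1.3), and those who withdraw after dosing should have the day 10 assessments then (section 3.2.3). This stands, and it is the main reason the point is small. It does not exclude a gap. Section 3.2.3 names trouble drawing blood as a ground for ending participation and promises only best effort for follow-up, and section 3.3.13 requires withdrawal if a prohibited drug becomes indicated.

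A second reply is that denominators and missing-result rules belong in a statistical analysis plan, which is not at hand. That is right for the missing-result rule, and its absence is not the complaint. The choice of ITT, however, is written in the protocol, and a later plan that moved ADA to the safety set would depart from it.

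Three stronger readings are tempting, and the protocol supports none of them:

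- **That untested patients count as not positive, so the rate is understated.** No section says so, nor whether percentages use all ITT patients or only those with a result. The rate can be diluted; it is not shown to be.
- **That the ADA rate decides on repeat dosing in a planned next trial.** Section 1.2 speaks only of a potential trial, and no threshold or decision depends on ADA.
- **That the table of patients turning positive after a negative baseline is diluted too.** It promises only a count. The set still matters for whom it covers, but no stated percentage is at risk.

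Finally, the baseline table differs: an undosed patient with a valid pre-dose sample belongs in it.

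**Conclusion.** The point holds as a poorly fitting analysis set for a safety endpoint, at odds with the protocol's own classification of ADA and its own safety set. The numerical consequence is conditional. It needs at least one randomized patient who is undosed or lacks a day 10 result, that patient kept in the denominator, and at least one positive patient. The day 10 percentage then falls by a relative m/N: one sixth in an arm of 6 for one such patient, one third for two. If all are dosed and sampled, the effect is nil. The values of m and x are assumptions.

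Severity is minor. ADA is exploratory and descriptive, at most 12 patients are involved, the sampling uncertainty is much larger than the shift, and individual ADA data are listed, so a reader could rebuild the table.

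**What to change.** In section 3.6.2.8 and the matching synopsis paragraph:

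1. Show the day 10 table, and the table of patients turning positive after a negative baseline, on the safety set by dose received.
2. Base day 10 percentages on dosed patients with evaluable results at both baseline and day 10. For the second table, use dosed patients who were negative at baseline and have a day 10 result.
3. Report the number of dosed patients without the needed result beside each table, by arm and overall.
4. Let the baseline-positive table use all patients with a valid baseline sample.

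The cost is a changed set name and a sentence or two on denominators, in two places. No extra samples or patients are needed. The small downside is that denominators may differ between tables, and undosed patients would appear only in the baseline table and the listings.
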